The NCEH laboratory will perform the analyses of serum PFAS according to the biochemical analytical plan (Attachment 2) and approved laboratory methods (Kuklenyik 2015). The NCEH laboratory staff will also aliquot and ship blood and serum specimens to participating laboratories for the analyses of the effect biomarkers according to the plan. The recipient will store the urine samples and conduct analyses at a later date when more knowledge is gained about urinary PFAS and effect biomarkers and until the laboratory methods are developed. Residual blood and urines will be archived at NCEH so that additional PFAS or effect biomarkers can be analyzed as new knowledge and analytical methods become available.

23 3.6.5 Questionnaire

Each adult participant, and a parent of the child participant, will complete a questionnaire during theappointment for the blood draw.

26 3.6.5.1 Children and Parents

27 Study staff will request that the parents of the child participant complete the questionnaire. The 28 questionnaire will obtain demographic information (e.g., education, primary occupation), residential history, water consumption habits, medical history of the mother and child, the child's medications, the mother's reproductive history (including maternal age at birth of the participating child) and any occupational exposures the mother may have had to PFAS. The questionnaire will be administered in two formats: a form for the child whose parent is not also a participant (Attachment 15), and an abbreviated form for the child whose parent is also an adult participant (Attachment 15a).

6 The questionnaire will obtain the mother's and child's residential history in the study area, and the dates 7 and length of time of the pregnancy and breastfeeding of the child. The questionnaire will also obtain 8 information on the water consumption habits (including use of water for formula, juices, etc., bottled 9 water use) of the mother and child when they resided in the study area. Information on the mother's 10 workplaces in the study area (location and dates) and the child's daycare and schools in the study area 11 (location and dates) will be obtained.

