Section B: Residential History and Drinking Water Exposures

This next set of questions is about the child and the child's birth mother. If you are not her, we can follow up after this interview with a quick phone call to complete the questionnaire.

B1. What is the main source of tap water in your home?

____Public water system

____Private well

____Other: specify _____

____Don't know

_____Refused to answer

B2. On average, how many 8 oz. cups of tap water or beverages prepared with tap water does your child currently drink per day at home?

____ cups

____Doesn't drink tap water

____Don't know

____Refused to answer

Note: 1 cup = 8 oz.; 2 cups = 1 pint (16 oz.); 4 cups = 1 quart (32 oz.); 16 cups = 1 Gallon (128 oz.

B3. On average, how many 8 oz. cups of tap water or beverages prepared with tap water do you currently drink per day at home?

____ cups

____Doesn't drink tap water

____Don't know

Refused to answer

Note: 1 cup = 8 oz.; 2 cups = 1 pint (16 oz.); 4 cups = 1 quart (32 oz.); 16 cups = 1 Gallon (128 oz.

B4. What was your previous address?

Street	Apt	
City	State	Zip Code:

B5. When did you move into your previous address? Month____ Year_____

B6. What was the main source of tap water at that address?

____Public water system

____Private well

____Other: specify _____

____Don't know

_____Refused to answer

B7. On average, how many 8 oz. cups of tap water or beverages prepared with tap water did your child drink per day when living at your previous address?

____ cups

_Don't drink tap water

Don't know

____Refused to answer

____Your child did not live at this address

Note: 1 cup = 8 oz.; 2 cups = 1 pint (16 oz.); 4 cups = 1 quart (32 oz.); 16 cups = 1 Gallon (128 oz.

B8. Have you or your child lived at any other address since January 2000?

___Yes

__No → go to Section C

____Don't know \rightarrow go to Section C

____Refused to answer \rightarrow go to Section C

B9. Please fill out the table below for these other residences where you or your child lived since January 2000.

Street Address, City, State	Did your	Your child's average	Move in	Main source of
	child live	consumption of tap	(mm/yy)	tap water at
	at this	water per day (# cups)		this address
	address?	at this address		(public water
				system or
				private well?)

Note: 1 cup = 8 oz.; 2 cups = 1 pint (16 oz.); 4 cups = 1 quart (32 oz.); 16 cups = 1 Gallon (128 oz.

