B10. When [you were/the child's birth mother was] pregnant with your child, on average how many 8 oz. cups of tap water or beverages prepared with tap water did [you/she] drink per day?

____ cups

____Didn't drink tap water

____Don't know

____Refused to answer

B11. When [you were//the child's birth mother was] breastfeeding your child, on average how many 8 oz. cups of tap water or beverages prepared with tap water did [you/she] drink per day?

- cups
- ____Didn't drink tap water
- ____Don't know
- ____Refused to answer
- ____Did not breastfeed my child

Section C: History of Potential Exposure Modifiers

This next set of questions is about the child and the child's birth mother. If you are not her, we can follow up after this interview with a quick phone call to complete the questionnaire.

- C1. [Have you/Has the birth mother] ever had a blood transfusion?
- ____Yes → Please specify how many times you had a blood transfusion______
- ___No →go to Question C3
- ____Don't know →go to Question C3
- ____Refused to answer →go to Question C3
- C2. When did [you/she] last have a blood transfusion? month/year
- C3. Has your child ever had a blood transfusion?
- ____Yes ightarrow Please specify how many times your child had a blood transfusion______
- ___No →go to Question C5
- ____Don't know →go to Question C5
- ____Refused to answer →go to Question C5
- C4. When did your child last have a blood transfusion?
- _____month/year
- C5. [Have you/Has the birth mother] ever donated blood?

___Yes

___No →go to Question C8

- ____Don't know →go to Question C8
- ____Refused to answer →go to Question C8
- C6. When did [you/the birth mother] last donate blood? _____ Month/Year

C7. On average, how often [do you/does the birth mother] donate blood in a year?

- C8. Has your child ever donated blood?
- ____Yes → Please specify how many times your child has donated blood______
- ___No \rightarrow go to Question D1.
- ____Don't know \rightarrow go to Question D1.
- ____Refused to answer \rightarrow go to Question D1.
- C9. When did your child last donate blood?
- _____ Month/Year

C10. On average, how often does your child donate blood in a year?

_____times

Section D: Occupational History

This next set of questions is about the child's birth mother. If you are not her, we can follow up after this interview with a quick phone call to complete the questionnaire.

D1. What is [your/the child's birth mother's] primary occupation?

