D2. On average, how many 8 oz. cups of tap water or beverages prepared with tap water do you currently drink per day at work?

____ cups

- ____Don't drink tap water
- ____Don't know
- ____Refused to answer

D3. Please fill out the table below for each job that lasted one month or more starting from the present and working back to 2000.

Job information	Job 1	Job 2	Job 3	Job 4
a. Where did the child's mother work				
(City, State)				
b. Name of the employer				
c. Start date (month, year)				
d. End date (month, year)				
e. Job title/description				
f. Did the child's mother work as a	Yes	Yes	Yes	Yes
firefighter?	No go to question g.	No go to question g.	No go to question g.	No go to question g.
If the child's mother worked as a	Yes	Yes	Yes	Yes
firefighter, did she come into contact	No	No	No	No
with firefighting foam used for fires	Don't know	Don't know	Don't know	Don't know
that involve flammable liquids (also				
known as class B fires)?				
g. was this job in any of the following	Manufacturing of nonstick	Manufacturing of nonstick	Manufacturing of nonstick	
Industries?	cookware	cookware	COOKWARE	COOKWARE
	yes no	yesno	yesno	yes10
	Manufacturing of stain resistant	contings used on cornets	contings used on cornets	contings used on carpots
	coatings used on carpets,	unbolstony and other fabrics	upholstony and other fabrics	upholstory, and other fabrics
	uphoistery, and other fabrics	ves no	ves no	
	yes10	Manufacturing of water resistant	Manufacturing of water resistant	Manufacturing of water resistant
	clothing	clothing	clothing	clothing
	yes no	yesno	yesno	yesno
h. Did the child's mother work with or		Yes (Please	Yes (Please	Yes (Please specify the chemical)
around any chemicals at this job such	Yes (Please specify the chemical)	specify the chemical)	specify the chemical)	
as solvents, metals, asbestos, or				No
pesticides?	No	No	No	Don't know
	Don't know	n't know	Don't know	
i. Did the child's mother work with	Yes	Yes	Yes	Yes
radiation?	No	No	No	No

Job information	Job 5	Job 6	Job 7	Job 8
a. Where did the child's mother work				
(City, State)				
b. Name of the employer				
c. Start date (month, year)				
d. End date (month, year)				
e. Job title/description				
f. Did child's mother work as a	Yes	Yes	Yes	Yes
firefighter?	No go to question g.	No go to question g.	No go to question g.	No go to question g.
If child's mother worked as a				
firefighter, did she come into contact	Yes	Yes	Yes	Yes
with firefighting foam used for fires	No	No	No	No

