Section B: Residential History and Drinking Water Exposures

B1. On average, how many 8 oz. cups of tap water or beverages prepared with tap water does your child currently drink per day at home?

____ cups

____Didn't drink tap water

____Don't know

____Refused to answer

Note: 1 cup = 8 oz.; 2 cups = 1 pint (16 oz.); 4 cups = 1 quart (32 oz.); 16 cups = 1 Gallon (128 oz.)

B2. Please fill out the table below for all residences that your child has lived.

Street Address, City, State	Your child's	Move in	Main source of
	average	(mm/yy)	tap water at
	consumption of		this address
	tap water per		(public water
	day (# cups) at		system or
	this address		private well?)

B3. When [you were/the child's birth mother was] pregnant with your child, on average how many 8

oz. cups of tap water or beverages prepared with tap water did [you/she] drink per day?

____ cups

___Didn't drink tap water

____Don't know

____Refused to answer

B4. When [you were/the child's birth mother was] breastfeeding your child, on average how many 8

- oz. cups of tap water or beverages prepared with tap water did [you/she] drink per day?
- ____ cups
- ____Didn't drink tap water
- ____Don't know
- ____Refused to answer
- ____Did not breastfeed my child

Section C: History of Potential Exposure Modifiers

This next set of questions is for the child's birth mother about the child. If you are not her, we can follow up after this interview with a quick phone call to complete the questionnaire.

- C1. Has your child ever had a blood transfusion?
- ____Yes ightarrow Please specify how many times your child had a blood transfusion______
- ___No →go to Question C3
- ___Don't know →go to Question C3
- ____Refused to answer →go to Question C3
- C2. When did your child last have a blood transfusion?

_____month/year

- C3. Has your child ever donated blood?
- ____Yes → Please specify how many times your child has donated blood______
- ___No \rightarrow go to Section D.
- ____Don't know \rightarrow go to Section D.
 - ___Refused to answer \rightarrow go to Section D.
- C4. When did your child last donate blood? _____ Month/Year

C5. On average, how often does your child donate blood in a year?

Section D: Occupational History of the Child

This next set of questions is for the child's birth mother about the child. If you are not her, we can follow up after this interview with a quick phone call to complete the questionnaire.

D1. Has your child been employed for at least one month at a job?

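### Mother's tap-water intake in pregnancy and breastfeeding is asked as one daily total without place, so it cannot be reliably divided between home and workplace taps

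*Protocol*

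**What the plan says.** **Current intake** is tied to a place. Long-form B2 asks how much tap water "does your child currently drink per day at home". B3 asks the same of the mother, and D2 asks her current intake at work.

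**Past maternal intake** is not. B10 asks for one daily figure, in the words "pregnant with your child, on average how many 8 oz. cups of tap water or beverages prepared with tap water did [you/she] drink". B11 asks, for the time she was "breastfeeding your child, on average how many 8 oz. cups of tap water or beverages prepared with tap water" she drank. Short-form B3 and B4 (Attachment 15a) use the same wording, asking how many "cups of tap water or beverages prepared with tap water did [you/she] drink per day", again with no place.

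**The child's past intake.** B7 asks how much "did your child drink per day when living at your previous address", without B2's home limit. B9 and short-form B2 do tie the child's cups to the listed address. E2 and E3 ask day-care and school cups separately, with street address and dates.

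**Workplaces.** Section 3.6.5.1 promises information on the mother's "workplaces in the study area (location and dates) and the child's daycare and schools in the study area". D3 item a asks "Where did the child's mother work" and takes city and state. Other D3 items give employer name and dates for jobs back to 2000, but no street address and no cups per day.

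**Use.** Section 3.9 lists questionnaire data on water consumption as an input to each participant's estimated cumulative serum level. Section 3.10 makes that estimate the focus of the primary analyses.

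**The concern.** In utero and breastfeeding exposure is an eligibility route (section 3.2), and section 5 names the in utero period as a vulnerable window that modelling might reach. On the long form, B10 and B11 are the only items on how much the mother drank in the past. The same water need not have come from both taps: sections 2.3 and 3.5 foresee concentrations that vary within a distribution system and sites where private wells are contaminated. The communication messages in Attachment 5 count people who worked at the site as exposed, and section 2.2 reports serum levels rising with time spent at the Pease Tradeport. A total without place then leaves an unknown fraction to be assigned to each source.

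B7 raises a smaller question about the child. A parent could answer it as a whole-day total, including water that E2 or E3 also records.

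**Working it through.** The documents give no figure on this point, so there is nothing to reproduce. The check compares the items and then sizes the error under stated assumptions.

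**1. What each item supplies**

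| Item | Whose intake | Period | Place of intake |
|---|---|---|---|
| B2, B3 | child, mother | current | home |
| D2 | mother | current | work |
| B10, B11; short-form B3, B4 | mother | pregnancy, breastfeeding | not asked |
| B7 | child | previous address | not limited to home |
| B9; short-form B2 | child | listed residences | that address |
| E2, E3 | child | by start and end date | day care, school |
| D3 | mother's jobs | back to 2000 | city, state, employer; no cups |

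**2. Maternal intake.** Let V be total daily intake, w the share drunk at work, and c_h and c_w the home and work concentrations.

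- True dose = V[(1-w)c_h + w·c_w].
- Dose if the whole total is assigned to the home tap = V·c_h.
- Ratio = c_h / [(1-w)c_h + w·c_w].

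V cancels, so the ratio depends only on w and on the relation between the two concentrations. Since w is not in the documents, a range is shown.

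| Case | w = 0 | w = 0.25 | w = 0.5 |
|---|---|---|---|
| Home contaminated, work clean: 1/(1-w) | 1.00 | 1/0.75 = 1.33 | 1/0.5 = 2.00 |
| Work at half the home level: 1/(1-w/2) | 1.00 | 1/0.875 = 1.14 | 1/0.75 = 1.33 |
| Same water at both | 1.00 | 1.00 | 1.00 |

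If the home is clean and the workplace contaminated, the assigned dose is 0 for any w, while the true dose is V·w·c_w. Assignment to home can therefore err in either direction.

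**3. Child's intake in B7.** Let T be the child's whole-day intake and s the share drunk at day care or school.

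- If B7 is answered as T and E2/E3 is added: (T + sT)/T = 1 + s, which is 1.25 at s = 0.25 and 1.5 at s = 0.5.
- If B7 is answered as home intake only: [(1-s)T + sT]/T = 1, so there is no overlap.

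The documents give no s and do not say how the items will be combined.

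**The case against.** **The taps can be located.** A reader might infer that intake cannot be matched to any contaminated tap. That goes too far. B4, B5 and B9 give street addresses and move-in dates for earlier homes, and Section G gives pregnancy and breastfeeding dates. Employer, city, state and job dates will often locate a workplace, though less reliably for an employer with several sites or within a non-uniform system. What is missing is mainly the division of cups.

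**An analyst could borrow the current split.** B3 and D2 give a present-day home-to-work ratio that could be applied to the past, with sensitivity analysis, and the method may be set out in a plan not shown. Section 3.9 also uses measured serum, and earlier biomonitoring for validation where available. This has force: nobody is compelled to assign the whole total to one tap. But the pregnancies ended at least four years before, jobs may have changed, and an imputed share is weaker than a reported one.

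**School water is counted twice.** A reader might infer this as fact. B7 follows a question about the tap source at the same address, so it can be read as home intake, and no rule for adding it to E2/E3 is stated. It is a possible overlap on the long form only.

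**Bias through maternal employment.** A reader might infer that the error distorts the neurobehavioral results because employment is related to them. The documents do not state that relation, and error that varies with employment is not by itself error that varies with outcome. The point does not rest on it.

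**Short-form mothers.** They are also adult participants, and section 3.6.5.2 says the adult questionnaire (Attachment 16) covers occupational history and water habits. That form is not in the text at hand, so a lack of workplace detail cannot be asserted for them.

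**Conclusion.** The point holds as a limited and cheaply removed weakness of the forms. Maternal intake in pregnancy and breastfeeding is not separated by place, and D3 has neither workplace address nor cups per day, so past intake cannot be reliably apportioned between home and workplace taps when their PFAS levels differ. With all intake assigned to a contaminated home and a clean workplace, the overstatement is 1.33-fold at an assumed work share of 0.25 and 2-fold at 0.5. With only the workplace contaminated, home assignment gives zero dose. With the same water at both, as section 2.4 foresees for a mixed supply, there is no error. The size thus depends on the unknown work share, on how the sites' taps differ, and on how the analyst assigns the total. B7 is ambiguous and may overlap with E2/E3; B9 and short-form B2 are sound.

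**What to change.** - Split long-form B10 and B11, and short-form B3 and B4, into cups at home, at work and elsewhere.
- Limit B7 to intake at home, as B2 does. Leave B9 and short-form B2 unchanged.
- Add a workplace street address to D3 item a, at least for jobs in the study area.
- Compute each dose with the water concentration of its own source, then sum home, work, day-care and school contributions.
- Check that Attachment 16 records workplace address and intake for mothers who are adult participants.

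The cost is rewording of existing items and one more field per relevant job, with a slightly longer interview. Recall of cups by place many years back will be imprecise, so a don't-know option should be kept for each part. The forms still carry placeholder approval numbers, and a split not asked at interview is hard to recover later.

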Among PFOA, PFOS, PFHxS and PFNA concentrations, water consumption had the strongest effect on PFHxS serum levels. In particular, water consumption had the highest effect on PFHxS serum levels among persons aged \leq 19 years (β = 0.31, SE = 0.15, marginal effect = 36.4%). Geometric mean PFOS and PFOA serum levels were also higher among persons who drank \geq 4 cups of water per day compared with those who drank <4 cups per day (NH DHHS 2016, Daly 2018). Linear trends were observed for geometric mean serum levels of PFOS, PFOA, and PFHxS and increasing time spent at the Pease Tradeport. The trend was strongest for PFOS and PFHxS (NH DHHS 2016, Daly 2018).

8

9 2.3 Selection of Sites

10 Possible candidate sites include communities whose drinking water was impacted by AFFF use at military

11 bases or by industrial PFAS emissions. The criteria for selecting study sites would include:

- 12 1. Documented past or present PFAS drinking water concentrations at the tap,
- 13 2. The magnitude of past or present PFAS concentrations at the tap,
- 14 3. Size of the population exposed,
- 15 4. Amount of information available on the contaminated drinking water system or private wells, and
- 16 5. If biomonitoring for PFAS has previously occurred at the site.

In order to determine the feasibility of a site for inclusion in the multi-site study, information on thefollowing parameters should be included in the application

 For public water systems using ground water sources, enumeration of supply wells that provided drinking water to the site. Information on each supply well should include years of operation, well capacity, and daily or monthly pumping rates. This information can be used to determine the monthly proportion of the total water supply provided by each well during the period when PFAS contamination occurred. Information is also necessary about changes to the water system (e.g., closure of contaminated supply wells) after the contamination was detected.

25 2. For a water system supplied by surface water, characteristics of this source.

- For a water system purchasing water from another system, characteristics of this source, the
 period of time purchased, and daily or monthly amount purchased in order to determine the
 proportion of the total water supply provided by the purchased water.

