The residual blood specimens will be stored with the study-generated ID only. ATSDR will keep a separate dataset that can link the study ID with the participant's name. If participants change their minds later about letting their blood used for additional analyses, they can contact ATSDR and we will remove their specimens. We do not plan to provide participants the results of these future tests, but we may contact them if we learn something that is important.

27 3.8.7 Future Exploratory Analyses

- 1 CDC IRB approval will be sought for this additional research either as a protocol amendment or under a
- 2 new research protocol prior to undertaking this plan.

3 **3.9 Exposure Estimation**

4 The study will use the fasting serum PFAS measurements obtained from study participants to estimate 5 exposures. In addition, the study will estimate each participant's cumulative PFAS serum level, using:

- PFAS serum measurements obtained in the study,
- Historical reconstruction of PFAS concentrations in the drinking water consumed by the
 participant,
- 9 Questionnaire data on the participant's consumption of PFAS-contaminated drinking water and
 10 factors that might affect PFAS serum levels,

• Age-, sex-, and calendar year-specific "background" PFAS serum levels from NHANES, and

12 • Physiologically based pharmacokinetic (PBPK) models.

13 If previous PFAS serum measurements are available for some of the participants (e.g., from a 14 biomonitoring program), then these results will be used to validate the modeled historical PFAS serum 15 estimates.

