Organize community meeting for former NH DHHS participants and other community members to announce the study	 Mail invitation letters and study fact sheet to recruits Organize a public meeting at the appropriate/suitable venue Use Multi-site CAP and local contacts to distribute material about upcoming meeting to schools, employers, and other stakeholders. 	Study PIs, study staff	After OMB approval 2 months after OMB approval	Provide a forum for potential participants to find out more about the study and have study investigators answer questions.

Agency for Toxic Substances and Disease Registry (ATSDR)

Multi-site Study

Overarching Communications Messages

- ATSDR is conducting the Multi-site PFAS Study:
 - to learn more about the human health effects of exposures to drinking water contaminated with perfluoroalkyl substances (PFAS), and
 - to identify issues that must be addressed prior to starting a future multi-site health study of PFAS-contaminated drinking water.
- The Multi-site Study will include children aged 4-17 years and adults aged ≥18 years who were exposed to the contaminated drinking water at the [insert site]. Persons will be eligible for the study if they lived in a home, worked or attended childcare at the site, were exposed in utero or during breastfeeding, that was served by a PFAS-contaminated public water system or private well.
- The Multi-site Study will recruit 6,000 adults and 2,000 children combined from the sites exposed to the PFAS-contaminated drinking water.
- The Multi-site Study will determine the participant's blood levels of PFAS as well as health indicators such as cholesterol levels, liver function, thyroid function and immune function. The participant's test results will be provided to the participant along with information on how to interpret the results.
Agency for Toxic Substances and Disease Registry (ATSDR)

Multi-site Study

Press Release - Launch

For Immediate Release:

Contact: ATSDR Media Office

[contact]

ATSDR launches a health study of adults and children exposed to drinking water contaminated with perfluoroalkyl substances ("PFAS")

The Agency for Toxic Substances & Disease Registry (ATSDR) is starting a study to determine the health effects of exposures to contaminated drinking water serving [insert site]. The public drinking water system at [insert site] was contaminated with perfluoroalkyl substances ("PFAS") from [insert as applicable].

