	yesno	yesno	yesno	yesno
	Manufacturing of water resistant	Manufacturing of water resistant	Manufacturing of water resistant	Manufacturing of water resistant
	clothing	clothing	clothing	clothing
	yesno	yesno	yesno	yesno
h. Did child's mother work with or	Ves (Please specify the chemical)	Yes (Please	Yes (Please	Yes (Please specify the chemical)
around any chemicals at this job such	res (riease specify the chemical)	specify the chemical)	specify the chemical)	
as solvents, metals, asbestos, or				No
pesticides?		No	No	Don't know
		n't know	Don't know	
i. Did child's mother work with	Yes	Yes	Yes	Yes
radiation?	No	No	No	No

This next questions are about your child.

D4. Has your child been employed for at least one month at a job?

____Yes

____No \rightarrow go to Section E.

Job information	Job 1	Job 2	Job 3
a. Where did your child work?			
(City, State)			
b. Name of the employer			
c. Start date (month, year)			
d. End date (month, year)			
e. Job title/description			
f. Did your child work with or	Yes (Please specify)	Yes (Please specify)	Yes (Please specify)
around radiation or any chemicals			
at this job such as solvents, metals,	No	No	No
asbestos, or pesticides?	Don't know	on't know	Don't know

D5. On average how many 8 oz. cups of tap water or beverages prepared with tap water did [he/she] drink per day at work?

- ____ cups
- ____Didn't drink tap water
- ____Don't know
- ____Refused to answer

Note: 1 cup = 8 oz.; 2 cups = 1 pint (16 oz.); 4 cups = 1 quart (32 oz.); 16 cups = 1 Gallon (128 oz.)

Section E: Child's Daycare/School History

E1. Did your child attend day care?

____Yes

____No \rightarrow go to Question E3

____Don't know \rightarrow go to Question E3

_____Refused to answer \rightarrow go to Question E3

E2. Please fill out the table below for the day care centers your child attended.

Day care	Street Address, City, State	Start	End	Child's average
(name)		Date	Date	consumption of tap
		(mm/yy)	(mm/yy)	water per day (# cups)

Note: 1 cup = 8 oz.; 2 cups = 1 pint (16 oz.); 4 cups = 1 quart (32 oz.); 16 cups = 1 Gallon (128 oz.)

E3. Please fill out the table below for the schools your child has attended. If your child was home schooled, please go to Section F

School (name)	Street Address, City, State	Start	End	Child's average
		Date	Date	consumption of tap
		(mm/yy)	(mm/yy)	water per day (# cups)

Note: 1 cup = 8 oz.; 2 cups = 1 pint (16 oz.); 4 cups = 1 quart (32 oz.); 16 cups = 1 Gallon (128 oz.)

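### The child questionnaires' day-care and school tables do not record how often the child attended, so that part of the primary exposure must rest on imputed attendance

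*Protocol*

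**What the plan says.** Section E of the long child form (Attachment 15) has two tables. E2 begins "Please fill out the table below for the day care centers your child attended" and E3 begins "Please fill out the table below for the schools your child has attended". Their columns are the name of the place, its address, start and end dates by month and year, and the child's average tap-water intake, expressed as "water per day (# cups"). There is no column for days per week, hours per day, or weeks or months per year. Section E of the short form (Attachment 15a) repeats both tables. E3 in both forms also carries the instruction "If your child was home schooled, please go to Section F".

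Section 3.6.5.1 describes the information sought on "the child's daycare and schools in the study area" as location and dates only. Intake at home is asked separately in Section B of each form.

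Section 3.9 lists "Questionnaire data on the participant's consumption of PFAS-contaminated drinking water" among the inputs to each participant's cumulative serum estimate, together with the serum measured in the study. Section 3.10 makes estimated cumulative serum the focus of the primary analyses.

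**The concern.** For water drunk at day care, the amount taken in over a year is cups per attended day multiplied by days attended. The form collects the first factor, in an undefined unit, and omits the second. Two children with the same cups and dates, one attending two days a week and the other five, cannot be told apart. Nor can the analyst tell a parent who answered per attended day from one who averaged over the calendar week.

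The item is never collected, so an analysis plan could choose an imputation rule but could not supply the missing data. What is at stake is the ranking of children on the day-care part of the primary exposure. Section 2.2 gives some reason to care: at Pease, serum PFOS, PFOA and PFHxS rose with "increasing time spent at the Pease Tradeport".

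The E3 skip is a separate weakness and needs no assumption. A child home schooled in some years and at school in others can be sent past the whole school table, which loses the addresses and dates of the schools attended.

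**Working it through.** The protocol states no figure on this point, so there is nothing to reproduce. Attendance and cup counts below are assumptions; the documents give neither.

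**Step 1: day-care component alone.** Error factor = days per week imputed / days per week attended.

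| True days | 5 imputed | 7 imputed (answer read as per calendar day) |
|---|---|---|
| 1 | 5/1 = 5.0 | 7/1 = 7.0 |
| 2 | 5/2 = 2.5 | 7/2 = 3.5 |
| 3 | 5/3 = 1.67 | 7/3 = 2.33 |
| 4 | 5/4 = 1.25 | 7/4 = 1.75 |
| 5 | 1.0 | 7/5 = 1.4 |

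No section adopts the 7-day reading. That column shows only what the undefined unit would permit.

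**Step 2: total intake when home water is also contaminated.** Let c be cups per attended day at day care and h be cups per day at home, with both waters at the same PFAS concentration (assumed). Error factor = (c × imputed + 7h) / (c × true + 7h). For 5 days imputed and 2 true:

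- c = 1, h = 1: (5 + 7)/(2 + 7) = 12/9 = 1.33
- c = 1, h = 2: (5 + 14)/(2 + 14) = 19/16 = 1.19
- c = 2, h = 1: (10 + 7)/(4 + 7) = 17/11 = 1.55
- c = 2, h = 2: (10 + 14)/(4 + 14) = 24/18 = 1.33
- h = 0 (clean home water): 5/2 = 2.5

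**Step 3: which children get the full factor?** Only those with h = 0. Section 3.2.1 admits children who resided in the affected area or were exposed in utero or by breastfeeding. The Overarching Communications Messages in the recruitment materials admit those who "lived in a home, worked or attended childcare at the site". A child exposed solely at day care is therefore eligible under the second text but not under the first, and the two need reconciling.

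**Step 4: school.** If the school year is about 170 to 190 days (assumed), attendance differs between full-time pupils by at most 190/170 = 1.12-fold. A common factor applied at analysis would deal with most of this. Part-time day care is where the missing item can reorder children. For school, the undefined unit and the skip matter more.

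**Step 5: how far measured serum helps.** Section 3.2.1 cites half-lives of about 3 years for PFOA and PFOS and about 5 years for PFHxS. After 12 years without exposure, the fraction left is 2^(−12/3) = 6% and 2^(−12/5) = 19%. Serum measured in an adolescent therefore says little about a day-care dose received in early childhood.

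**The case against.** The strongest reply is that the 2.5-fold factor is not the error in a child's dose. It belongs to one component, under an attendance pattern that the documents do not give. Most eligible children qualify by residence and have their home intake recorded. This stands, and Step 2 reflects it.

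A reader might also infer that the gap can never be repaired. The documents do not support that. The contact form (Attachment 10) tells participants that they may be contacted again with clarifying questions, and it collects three outside contacts. Day-care names and dates will be on file, so a targeted call is possible. Recall would be older, and asking once at interview is simpler.

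Measured serum enters the cumulative estimate (Section 3.9) and is analysed in its own right (Section 3.10). This constrains the error for recent exposure, but less for exposure long past (Step 5).

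Two further inferences go beyond the text. One is that intake will be spread over all 365 days; Section 3.9 leaves the modelling detail to the recipient and prescribes no such rule. The other is that attendance tracks parental employment and so confounds the neurobehavioural outcomes. That is conjecture, and parental education and household income are collected.

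Finally, the Pease trend is with time spent, which Section 2.2 does not define. It may mean years, which the start and end dates already capture.

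**Conclusion.** The omission is plain in both forms, and it reaches the primary exposure. Its size is conditional. Imputing 5 days for a 2-day child overstates the day-care component 2.5-fold (1.0 to 5.0 across 5 down to 1 true days). With home water at the same concentration and 1 to 2 cups at each place, total intake is overstated about 1.2- to 1.55-fold. If attendance equals what is imputed, or if intake is both reported and used as a calendar-day average, this source adds no error. The form cannot show which children those are.

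A reader might conclude that children's doses are generally wrong by 2.5-fold or more. The documents do not support that: it would need clean home water, and Section 3.2.1 does not make day-care attendance alone a route to eligibility. No loss of power or share of explained variance can be put on the gap either, because the spread of attendance and of the other determinants of dose is not stated.

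The gap is hard, not impossible, to repair later. The E3 skip is a separate wording fault that holds without any assumption. Taken together, this is a cheap improvement and not a threat to the study's validity.

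**What to change.** In Attachments 15 and 15a, Section E:

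- Add to E2 and E3 the columns *days per week attended* and *weeks (or months) per year*.
- Head the intake column *cups per attended day, at this place*.
- Reword the E3 skip to *if your child has never attended a school outside the home, go to Section F*.
- Bring the description in Section 3.6.5.1 into line, and state in Section 3.9 that intake is multiplied by attendance in the serum model.

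A days-per-week item for the child's job table is optional. Separately, reconcile the eligibility wording in Section 3.2.1 with the communications messages, so that it is clear whether children exposed only at day care are in the study.

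The cost is about a minute more of interview. The OMB numbers on both forms are still placeholders, so the change can be made before the forms are fixed. Parents' recall of attendance will be imperfect, but an approximate answer is better than one value imputed for every child.
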